1.4 STUDY PLAN

Please refer to Section 1.2 of the study protocol for study flow chart. The graphical study design is provided in [Figure 1](#)

Figure 1 – Graphical Study

Design

★ Treatment consisting of 2 injections of 1.5 mL each of SAR440340 or placebo

¹ Variable treatment period determined by either completion of a 52 week treatment duration or the end of treatment of the last patient completing planned treatment (EOT visit), whichever occurs earlier

² End of Treatment (EOT) visit to occur 2 weeks after last administration of IMP

1.5 MODIFICATIONS TO THE STATISTICAL SECTION OF THE PROTOCOL

A secondary efficacy population is added in the SAP. This secondary population includes all patients in the mITT population (the primary efficacy population) with baseline eosinophil values $\geq 250/\text{mm}^3$.

A tertiary endpoint, proportion of SGRQ responders at Week 24, is added. The SGRQ responders are patients whose Week-24 SGRQ total scores decrease 4 points or more from baseline. The corresponding efficacy analysis for this endpoint is logistic regression detailed in [Section 2.4.4.3.2](#).

1.6 STATISTICAL MODIFICATIONS MADE IN THE STATISTICAL ANALYSIS PLAN

Not applicable.

2 STATISTICAL AND ANALYTICAL PROCEDURES

2.1 ANALYSIS ENDPOINTS

2.1.1 Demographic and baseline characteristics

The baseline value is defined as the last available value prior to the first dose of IMP. For patients randomized but not treated, the baseline value is the last available value up to randomization.

All baseline safety and efficacy parameters (apart from those listed below) are presented along with the on-treatment summary statistics in the safety and efficacy sections ([Section 2.4.5](#) and [Section 2.4.4](#)).

Demographic characteristics

The following demographic characteristics will be summarized separately by treatment and overall:

- Sex (Male, Female)
- Race (American Indian or Alaska Native, Asian, Black or African American, Native Hawaiian or Other Pacific Island, White, Multiple, Unknown, Not Reported)
- Age (years)
- Age groups (<60, ≥60-<65, ≥65-<70, ≥70-≤75 years)
- Ethnicity (Hispanic or Latino, non-Hispanic or Latino, Unknown, Not Reported)
- Region (East Europe: Poland, Russia, Turkey and Ukraine; Latin America: Argentina and Chile; Western Countries: USA, Canada, Australia and Germany)
- Body weight (kg)
- Body weight group (<70, ≥70-<90, ≥90 kg)
- Body mass index (BMI, kg/m²)
- BMI group (<25, ≥25-<30, ≥30-<35, ≥35 kg/m²)

Alcohol use will also be included in this summary as alcohol drinking frequency (Never, Occasional, At least daily, At least weekly, At least monthly) and number of standard alcohol drinks on a typical day when drinking (1 or 2, >2).

Medical or surgical history

Medical (or surgical) history includes all the relevant medical (or surgical) history during the lifetime of the patient.

This information will be coded using the version of Medical Dictionary for Regulatory Activities (MedDRA) in effect at Sanofi at the time of database lock.

COPD and allergic comorbidity medical history will be summarized separately, including:

- Hospitalization because of severe respiratory infection (Yes, No)
- Long stay in neonatal intensive care unit (Yes, No)
- Diagnosed with bronchopulmonary dysplasia (Yes, No)
- Family history of COPD (Yes, No)
- Exposed to occupational/environmental pollutants (Yes, No), if Yes, summarize years of exposure.
- Comorbidities (Yes, Ongoing for each): Asthma, Bronchiectasis, Nasal polyps, Chronic sinusitis, Atopic dermatitis, Allergic conjunctivitis, Allergic rhinitis, Food allergy, Hives, Eosinophilic esophagitis, Hypersensitivity to aspirin, Hypersensitivity to NSAID, Atopic disease (Nasal Polyps or Chronic sinusitis or Atopic dermatitis), Allergies (Allergic conjunctivitis or Allergic rhinitis or Food allergy), Hypersensitivity (Hypersensitivity to NSAID or Hypersensitivity to Aspirin)

Disease characteristics at baseline

The following baseline disease characteristics will be summarized by treatment group separately and overall:

- Age at diagnosis of COPD (years)
- Time since diagnosis of COPD at randomization (years)
- Time since last COPD exacerbation at randomization (months)
- Number of moderate or severe COPD exacerbations experienced in the past one year before screening visit (quantitative variable and qualitative variable: 0, 1, 2, 3, ≥ 4)
- Number of moderate COPD exacerbations experienced within 1 year before screening visit (Among the moderate COPD exacerbations, how many required use of (1) systemic corticosteroids and antibiotics, (2) only systemic corticosteroids, (3) only antibiotics. And if systemic corticosteroids were used to treat the moderate COPD exacerbations, the total number of treatment days in the past one year, which will be further broken down to the treatment days using oral, intravenous and intramuscular systemic corticosteroids)
- Number of severe COPD exacerbations experienced within 1 year before screening visit (Among the severe COPD exacerbations, how many required use of (1) systemic corticosteroids and antibiotics, (2) only systemic corticosteroids, (3) only antibiotics. And if systemic corticosteroids were used to treat the severe COPD exacerbations, the total number of treatment days in the past one year, which will be further broken down to the treatment days using oral, intravenous and intramuscular systemic corticosteroids)

- Smoking history (Former, Current), time since cessation of smoking (years) and smoking quantity in pack-years
- Baseline spirometry data including pre-bronchodilator (pre-BD) FEV1 (L), post-bronchodilator (post-BD) FEV1 (L), pre-BD and post-BD FEV1 percent predicted (%), pre-BD and post-BD FEV1/FVC (%), pre-BD and post-BD FVC (L) and pre-BD and post-BD FVC percent predicted (%)
- Baseline COPD Assessment Test (CAT) score
- Baseline Euroqol Questionnaire (EQ-5D-5L) score
- Baseline St. George's Respiratory Questionnaire (SGRQ) score
- Baseline Exacerbations of Chronic Obstructive Pulmonary Disease Tool (EXACT) score
- Baseline blood eosinophil count ($< 250 /\text{mm}^3$ and $\geq 250 /\text{mm}^3$)
- Eosinophil count for stratification ($< 250 /\text{mm}^3$ and $\geq 250 /\text{mm}^3$)
- Background therapy containing ICS (Yes/No); if ICS were used, dose of ICS (quantitative variable and qualitative variable: medium, high*)
**Medium: total daily dose of fluticasone = 500 or 460 mcg; high: total daily dose of fluticasone = 1000 or 920 mcg*
- Type of background therapy (Double therapy: LABA + LAMA, ICS + LABA, or ICS + LAMA; Triple therapy: ICS + LABA + LAMA)

Baseline biomarkers

Baseline values of biomarkers, including eosinophils, neutrophils, total IL33, sST2, calcitonin, PARC, eotaxin-3, total IgE, fibrinogen, and FeNO (optional, both pre-BD and post-BD), will be summarized. Eosinophils will be further summarized as

- Baseline blood eosinophil count (quantitative in $< 250 /\text{mm}^3$ and in $\geq 250 /\text{mm}^3$)
- Eosinophil count for stratification (quantitative in $< 250 /\text{mm}^3$ and in $\geq 250 /\text{mm}^3$)
- Baseline blood eosinophil count (quantitative and qualitative < 150 , $150-300$, $\geq 300 /\text{mm}^3$)

Any technical details related to computation, dates, and imputations for missing dates are described in [Section 2.5](#).

2.1.2 Prior or concomitant medications

Any medication or vaccine (including over-the-counter or prescription medicines, vitamins, and/or herbal supplements) that the participant is receiving from 3 months prior to screening visit to the end of study will be recorded in the electronic case report form (eCRF).

All medications will be coded using the World Health Organization-Drug Dictionary (WHO-DD) version currently in effect at Sanofi at the time of database lock.

- Prior medications are those the patient used prior to first IMP injection. Prior medications can be discontinued before first administration or can be ongoing during treatment phase.
- Concomitant medications are any treatments received by the patient concomitantly to the IMP, from the first administration of IMP to the last administration of IMP + 154 days.
- If applicable, post-treatment medications are those the patient took in the period from the last administration of IMP + 155 days to the end of the study.

A given medication can be classified in more than one category. Any technical details related to computation, dates, imputation for missing dates are described in [Section 2.5](#).

2.1.2.1 Background therapy

Requirements for background therapy prior to screening and during the study are described in [Section 1.1](#).

2.1.2.2 Reliever medication

Patients may administer albuterol/salbutamol or levalbuterol/levosalbutamol MDI as reliever medication as needed during the study. Nebulizer solutions may be used as an alternative delivery method. Usage of reliever medication will be recorded in the electronic diary.

Salbutamol/albuterol nebulizer and levosalbutamol/levalbuterol nebulizer use recorded in the electronic diary will be converted to number of puffs as shown on the following tables:

Table 2 - Salbutamol/Albuterol Nebulizer dose conversion

Salbutamol/Albuterol Nebulizer Solution Total Daily Dose (mg)	Number of Puffs*
2.5	4
5.0	8
7.5	12
10	16

*Conversion factor: salbutamol/albuterol nebulizer solution (2.5 mg) corresponds to 4 puffs

Example of salbutamol/albuterol nebulizer-to-puff conversion: Patient received 3 salbutamol/albuterol nebulizer treatments (2.5 mg/treatment) between 7 and 11 AM. Total daily dose = 7.5 mg or 12 puffs.

Table 3 - Levosalbutamol/Levalbuterol Nebulizer dose conversion

Levosalbutamol/Levalbuterol Nebulizer Solution Total Daily Dose (mg)	Number of Puffs*
0.63	2
1.25/1.26	4
1.89	6
2.5/2.52	8
3.15	10
3.75/3.78	12
4.41	14
5/5.04	16
5.67	18
6.25/6.30	20
6.93	22
7.50/7.56	24

*Conversion factor: levosalbutamol/levalbuterol nebulizer solution (1.25 mg) corresponds to 4 puffs

Example of levosalbutamol/levalbuterol nebulizer-to-puff conversion: Patient received 3 levosalbutamol/levalbuterol nebulizer treatments (1.25 mg/treatment) between 7 and 11 AM. Total daily dose = 3.75 mg or 12 puffs.

2.1.3 Efficacy endpoints

2.1.3.1 Primary efficacy endpoint(s)

The primary endpoint is the annualized rate of moderate-to-severe AECOPD over the treatment period.

Moderate exacerbations are recorded by the Investigator and defined as AECOPD that requires either systemic corticosteroids (such as intramuscular, intravenous or oral) and /or antibiotics.

Severe exacerbations are recorded by the Investigator and defined as AECOPD requiring hospitalization, emergency medical care visit or resulting in death.

2.1.3.2 Secondary efficacy endpoint(s)

The key secondary efficacy endpoint is the average change from baseline to Weeks 16, 20 and 24 in pre-bronchodilator FEV1.

The other secondary efficacy endpoint is the change from baseline to Week 24 in post-bronchodilator FEV1.

The third secondary efficacy endpoint is time to first moderate or severe AECOPD up to week 52.

2.1.3.3 Tertiary efficacy endpoint(s)

- Change from baseline at Week 24 in the patient-reported outcome including EXACT domain and total scores, EQ-5D-5L index score and Visual Analogue Scale (VAS) and SGRQ domain and total scores.
- Proportion of patients with a decrease from baseline of 4 points or more in the SGRQ total score (i.e. change from baseline ≤ -4) at Week 24.
- Average change from baseline to Week 16-24 in FVC (% predicted and absolute values in mL)
- Time to the first expanded AECOPD endpoint (moderate or severe AECOPD or study drug discontinuation [after week 4] due to lack of efficacy) up to week 52
- Time to first Clinically Important Deterioration (CID) as defined by decrease of >100mL from baseline in trough pre-BD FEV1 and/or deterioration in SGRQ by 4 units and/or moderate-to-severe AECOPD over the treatment period

2.1.3.3.1 Patient-reported outcomes

COPD Assessment Test (CAT)

The CAT is a short, validated, patient-completed questionnaire to assess the impact of COPD on health status (see [Appendix C](#)). It comprises 8 questions that cover a broad range of effects of COPD on patients' health. Each question is scored in a range between 0 (I am very happy) and 5 (I am very sad), with the higher end indicating a higher impact of COPD on the patient's wellbeing. The CAT total score, the sum of the 8 individual question scores, ranges from 0 (best) to 40 (worst). This score is collected only at screening and baseline to assess patient eligibility.

St. George's respiratory questionnaire (SGRQ)

St. George's Respiratory Questionnaire (SGRQ) is a 50-item PRO instrument developed to measure the health status of patients with airway obstruction diseases (see [Appendix E](#)). The questionnaire is divided into two parts: part one consists of eight items pertaining to the severity of respiratory symptoms in the preceding 4 weeks; part two consists of 42 items related to the daily activity and psychosocial impacts of the individual's respiratory condition.

The SGRQ yields a total score and three domain scores (symptoms, activity, and impacts). The total score indicates the impact of disease on overall health status. This total score is expressed as a percentage of overall impairment; 100 represents the worst possible health status and 0 indicates the best possible health status (minimal clinically important difference: -4 units). Likewise, the domain scores range from 0-100, with greater scores indicative of greater impairment. See [Appendix F](#) for the scoring algorithm.

This questionnaire is assessed at baseline and at weeks 4, 8, 12, 24, 36, 52, 60 and 72.

Exacerbations of chronic obstructive pulmonary disease tool (EXACT)

The EXACT is a 14-item daily diary designed to provide a direct measure of patient-reported symptoms of COPD exacerbation (see [Appendix B](#)) and covers the following domains:

- Breathlessness (5 items),
- Cough and sputum (2 items),
- Chest symptoms (3 items),
- Difficulty bringing up sputum (1 item),
- Tired or weak (1 item),
- Sleep disturbance (1 item), and
- Scared or worried (1 item).

It is completed each evening before bedtime.

The EXACT total score is an interval-level scale ranging from 0 to 100, where higher scores indicate a more severe condition.

Additional information can be obtained through 3 domain scores: Breathlessness (items 7, 8, 9, 10 and 11), Cough & Sputum (items 2 and 3), and Chest Symptoms (items 1, 5, and 6). These scores also range from 0 to 100, with higher scores indicating more severe symptoms. Note that items 4, 12, 13 and 14 do not correspond to a domain score.

Additional information related to computing scores and frequency, severity, and duration of events can be found in the *The Exacerbations of Chronic Pulmonary Disease Tool (EXACT) Patient-Reported Outcome (PRO) User Manual- Scoring guide* (Version 7.0), October 2014.

Baseline EXACT score as well as the post-baseline weekly scores are calculated as the mean within-patient score over the prior 7 days, with data present for a minimum of 4 of the 7 days. If fewer than 4 days of data are available in the 7-day window, the EXACT score cannot be calculated and will be considered as missing.

EQ-5D-5L

EQ-5D-5L is a standardized questionnaire developed by the EuroQol Group in order to provide a simple, generic measure of health for clinical and economic appraisal (1). EQ-5D is designed for self-completion by patients.

The EQ-5D consists of 2 pages - the EQ-5D descriptive system and the EQ VAS (see [Appendix D](#)). The EQ-5D descriptive system comprises 5 dimensions: mobility, self-care, usual activities, pain/discomfort and anxiety/depression. Each dimension has 5 levels: no problems, slight problems, moderate problems, severe problems, and extreme problems/unable. EQ-5D-5L health status will be converted into a single index value by using EQ-5D-5L crosswalk value sets based on UK population (2).

The EQ Visual Analogue Scale (VAS) records the respondent's self-rated health on a vertical visual analogue scale. The EQ VAS 'thermometer' has endpoints of 100 (Best imaginable health state) at the top and 0 (Worst imaginable health state) at the bottom.

This questionnaire is assessed at baseline and weeks 24, 52, 60 and 72.

2.1.3.4 Exploratory efficacy endpoint(s)

- Change from the average of measurements over baseline to the average of measurements over Weeks 10-12 and over Weeks 22-24 in sleep parameters (total sleep time, wake after sleep onset, overnight activity counts), for patients in US and Canada only
- Change from the average of measurements over baseline to the average of measurements over Weeks 10-12 and over Weeks 22-24 in activity parameters (daytime activity counts, percent of time spent in sedentary activity, percent of time spent in moderate to vigorous physical activity), for patients in US and Canada only
- Change from the average of measurements over baseline to the average of measurements over Weeks 10-12 and over Weeks 22-24 in FEV1 measured at home, for patients in US and Canada only

The daily/nightly actigraphy (activity, sleep) and daily home spirometry data will be first averaged in the designated analysis windows and the resulted averages are used to calculate the change from baseline.

2.1.4 Safety endpoints

The safety analysis will be based on the reported adverse events (AEs) and other safety information, such as clinical laboratory data, vital signs, electrocardiogram (ECG), etc.

Observation period

The observation period will be divided into 4 epochs:

- The **screening** epoch is defined as the time from the signed informed consent date up to the first administration of the IMP.
- The **treatment** epoch is defined as the time from the first administration of the IMP to the last administration of the IMP + 14 days.
- The **residual treatment** epoch is defined as the time from the last administration of the IMP + 15 days to the last administration of the IMP + 154 days.
- If applicable, the **post-treatment** epoch is defined as the time from the last administration of the IMP + 155 days to the patient's end of study (defined as last protocol-planned visit or the resolution/stabilization of all serious adverse events and adverse events with pre-specified monitoring).

The treatment-emergent adverse event (TEAE) period will include both **treatment** and **residual treatment** epochs.

The on-study observation period is defined as the time from the first administration of the IMP to the end of the study.

2.1.4.1 Adverse events variables

Adverse event observation period

- Pre-treatment adverse events are adverse events that developed or worsened or became serious during the screening epoch.
- Treatment-emergent adverse events are adverse events that developed or worsened or became serious during the treatment-emergent adverse event period.
- Post-treatment adverse events are adverse events that developed or worsened or became serious during the post-treatment epoch.

All adverse events (including serious adverse events and adverse events with pre-specified monitoring) will be coded to a lower-level term (LLT), preferred term (PT), high-level term (HLT), high-level group term (HLGT), and associated primary system organ class (SOC) using the version of MedDRA currently in effect at Sanofi at the time of database lock.

Adverse event of special interest (AESI) and other selected AE groupings will be searched based on criteria in [Table 4](#):

Table 4 - Criteria for adverse events of special interest and other selected AE groupings

AE Grouping	Criteria
AESI	
Anaphylactic reaction (medically reviewed)	Anaphylactic reaction algorithmic approach (Introductory Guide for Standardised MedDRA Queries (SMQs) Version 20.0): includes anaphylactic reaction narrow SMQ (20000021) terms and programmatic identification of cases based on occurrence of at least two preferred terms meeting the algorithm criteria occurring within 24 hours of each other. The latter cases identified using the algorithm will undergo blinded medical review taking into account the timing of events relative to each other and to IMP administration for final determination of anaphylactic reaction or not.
Hypersensitivity (medically reviewed)	SMQ hypersensitivity (20000214) narrow search or Preferred terms of pruritus or pruritus generalized and [AE corrective treatment/therapy='Y' or Action taken with IMP='Drug withdrawn' or Action taken with IMP='Drug interrupted'] followed by blinded medical review (documented process) for selection of relevant systemic events

AE Grouping	Criteria
Injection site reactions (serious/severe and lasting 24 hours or longer)	
HLT = 'Injection site reaction' and either with serious status or non-serious events with (AE end date/time-AE start date/time) ≥ 24 hours or ongoing and at least one of the following checked on the Injection Site Reaction Complementary Form:
 
 - Diameter of at least 10cm - Prevents daily activities - Presence of ulceration or necrosis - Operative intervention required
Infection	
Primary SOC = 'Infections and infestations' and meeting at least one of the following criteria
 
 - Serious status - 'Have any parental treatment (IV, Intramuscular, SC) been given for this event?' is answered Yes on eCRF Infection Event Form - 'Did this event require Prolonged Medication (greater than 14 Days)?' is answered Yes on eCRF Infection Event Form
Parasitic infection	Infection Type 'Parasitic' selected on eCRF Infection Event Form
Opportunistic infection	'Has the AE been assessed as opportunistic infection?' is answered Yes on eCRF Infection Event Form
Potential drug-related hepatic disorder	Drug-related hepatic disorders-Comprehensive search narrow SMQ (20000006)
Malignancy	Sub-SMQ (20000091)-Malignant or unspecified tumors
Pregnancy	'Pregnancy' or 'Partner Pregnancy' ticked on the Pregnancy eCRF.
Symptomatic overdose with IMP	'Overdose of IMP' and 'Symptomatic Overdose' are both ticked Yes on the Overdose eCRF
Symptomatic overdose with NIMP	'Overdose of NIMP' and 'Symptomatic Overdose' are both ticked Yes on the Overdose eCRF
Other selected AE grouping	
Injection site reaction	HLT = 'Injection site reaction'

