8.3.1 Adverse event of special interest

An adverse event of special interest (AESI) is an AE (serious or nonserious) of scientific and medical concern specific to the Sponsor's product or program, for which ongoing monitoring and immediate notification by the Investigator to the Sponsor is required. Such events may require further investigation in order to characterize and understand them. Adverse events of special interest may be added, modified or removed during a study by protocol amendment.

For these AESIs, the Sponsor will be informed immediately (ie, within 24 hours), per SAE notification described [Section 8.3.2](#), even if not fulfilling a seriousness criterion, using the screens in the eCRF.

Anaphylactic reactions, systemic allergic reactions that require treatment (refer to [Section 10.15](#) for definition of anaphylaxis).

- Anaphylactic reactions, systemic allergic reactions that require treatment (refer to [Section 10.15](#) for definition of anaphylaxis).
- Severe injection site reactions (ISR) that last longer than 24 hours

Note: A severe ISR (for AE reporting) is any event that meets one of the following criteria:

- With a diameter of at least 10 cm.
- Impacting daily activities.
- With ulceration or necrosis.
- For which operative intervention is required.
- Any infection meeting at least one of the following criteria:
 - Any serious infection (SAE).
 - Requires parenteral (IV, intramuscular, SC) antimicrobial therapy
Note: Antimicrobial therapy refers to antibiotic, antiviral, and antifungal agents.
 - Requires oral antimicrobial therapy for longer than 14 days.
 - Is a parasitic infection.
 - Is an opportunistic infection (see Appendix 15: List of Opportunistic Infections, [Section 10.16](#)).
- Significant ALT elevation.
 - ALT >3 x the upper limit of normal (ULN) associated with Total Bilirubin >2 x ULN;
or
 - ALT >5 x ULN in patients with baseline ALT ≤2 x ULN; or
 - ALT >8 x ULN if baseline ALT >2 x ULN.
- Malignancy
- Pregnancy of a female patient entered in a study as well as pregnancy occurring in a female partner of a male patient entered in a study with IMP/NIMP;
 - Pregnancy occurring in a female patient entered in the clinical trial or in a female partner of a male patient entered in the clinical trial. It will be qualified as an SAE only if it fulfills one of the seriousness criteria (see Appendix 3 [[Section 10.3](#)]).
 - In the event of pregnancy in a female participant, IMP should be discontinued.

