Hypersensitivity	
Allergic reaction is a potential risk associated with the administration of most therapeutic mAbs.
 
Acute allergic reactions may be defined as allergic reaction-mediated signs and symptoms experienced by patients during or shortly after the pharmacologic or biologic agent given. These reactions may present in a variety of ways, including dizziness, headache, anxiety, dyspnea, hypotension, tachycardia, pruritus, rash, urticaria/angioedema, flushing, nausea, or vomiting. Anaphylaxis may represent the most severe form of allergic reaction, but these events may also occur via non-IgE mediated mechanisms (eg, anaphylactoid reactions), or may occur via other immune-mediated mechanisms (eg, cytokine-mediated). Allergic reactions may begin within a few hours and persist up to 24 hours post dosing. Refer to Section 10.15 “Definition of Anaphylaxis”, which describes the clinical criteria for the diagnosis of anaphylaxis. Delayed onset or late phase hypersensitivity reactions (ie, Type 1 hypersensitivity reaction) may manifest between 10 and 12 hours post dosing.
 
Patients should be monitored for at least 30 minutes after IMP dose administration for any signs or symptoms of a hypersensitivity reaction throughout the study. Trained personnel and medications should be available to treat anaphylaxis or any severe allergic reaction if it occurs. Anaphylactic reactions, systemic allergic reactions that require treatment must be reported as an AESI with immediate notification (for further details, see Table 7). If an anaphylactic reaction, systemic allergic reaction requiring treatment occurs and is considered related to IMP by the investigator the study treatment should be permanently discontinued.
 
Anti-drug antibodies and PK samples will be collected near the onset and resolution of the AESI for any additional analysis.

Severe injection site reactions	
Based on the SC mode of administration of high doses of protein ISRs are considered as a potential risk for SAR440340.
 
Patients who experience an ISR must be closely monitored for the possibility of a more intense ISR with a future injection. Any severe ISR that lasts over 24 hours will be reported as an AESI with immediate

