- Convulsions (seizures, epilepsy, epileptic fit, etc)
- Development of drug dependence or drug abuse
- ALT >3 x the upper limit of normal (ULN) + total bilirubin >2 x ULN or asymptomatic ALT increase >10 x ULN
- Suicide attempt or any event suggestive of suicidality
- Syncope, loss of consciousness (except if documented as a consequence of blood sampling)
- Bullous cutaneous eruptions
- Cancers diagnosed during the study
- Chronic neurodegenerative diseases (newly diagnosed).

RECORDING AND FOLLOW-UP OF AE AND/OR SAE

AE and SAE recording

- When an AE/SAE occurs, it is the responsibility of the Investigator to review all documentation (eg, hospital progress notes, laboratory reports, and diagnostics reports) related to the event.
- The Investigator will then record all relevant AE/SAE information in the CRF.
- It is **not** acceptable for the Investigator to send photocopies of the participant's medical records to the Sponsor's representative in lieu of completion of the AE/SAE CRF page.
- There may be instances when copies of medical records for certain cases are requested by the Sponsor's representative. In this case, all participant identifiers, with the exception of the participant number, will be redacted on the copies of the medical records before submission to the Sponsor's representative.
- The Investigator will attempt to establish a diagnosis of the event based on signs, symptoms, and/or other clinical information. Whenever possible, the diagnosis (not the individual signs/symptoms) will be documented as the AE/SAE.

Assessment of intensity

The Investigator will make an assessment of intensity for each AE and SAE reported during the study and assign it to 1 of the following categories:

- **Mild:** An event that is easily tolerated by the participant, causing minimal discomfort and not interfering with everyday activities.
- **Moderate:** An event that causes sufficient discomfort and interferes with normal everyday activities.
- **Severe:** An event that prevents normal everyday activities. An AE that is assessed as severe should not be confused with a SAE. Severe is a category utilized for rating the intensity of an event; and both AEs and SAEs can be assessed as severe.

An event is defined as ‘serious’ when it meets at least 1 of the predefined outcomes as described in the definition of an SAE, NOT when it is rated as severe.

Assessment of causality

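### SAP Table 4 sets a higher daily-activities threshold for the injection site reaction AESI than protocol 8.3.1, so some reactions that sites must report as AESIs could fall outside the SAP's AESI category

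*SAP*

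**What the plan says.** **Protocol 8.3.1** lists as an AESI "Severe injection site reactions (ISR) that last longer than 24 hours". A note defines the term for this purpose: "A severe ISR (for AE reporting) is any event that meets one of the following criteria". The four criteria are a size limit (10 cm or more), "Impacting daily activities", ulceration or necrosis, and need for an operation. Table 6 states the site's duty: "Any severe ISR that lasts over 24 hours will be reported as an AESI with immediate" notification. Table 7 sets the time limit at 24 hours.

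**SAP 2.1.4.1, Table 4** defines the corresponding analysis category within the MedDRA high-level term for injection site reactions. Serious reactions enter on that status. Non-serious reactions enter if they last 24 hours or more, or are ongoing, and at least one of four boxes is ticked on the Injection Site Reaction Complementary Form. Three boxes match the protocol's criteria. The fourth reads "Prevents daily activities".

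**SAP 2.4.5.1** builds the AESI summary from the Table 4 criteria. **SAP 1.5**, which lists changes to the protocol's statistical section, mentions only an added efficacy population and an added SGRQ responder endpoint.

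**The concern.** The two lists are plainly meant to be the same list, and one item carries a different verb. If the verbs differ in meaning, sites report one event and the SAP tabulates a narrower one under the same name. The AESI incidence in the study report would then not correspond to the event defined in the protocol, and nothing in the SAP tells the reader so.

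Safety and tolerability is a secondary objective, and protocol Table 6 names ISRs as a potential risk of this product, which is given as two subcutaneous injections every 2 weeks. A reader of the report would take the AESI line as the count of reactions that met the protocol's definition.

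**Working it through.** The plan gives no figure to reproduce and no arithmetic applies. The check is a comparison of the texts.

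**1. The criteria side by side**

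| Element | Protocol 8.3.1 | SAP Table 4 |
|---|---|---|
| Combination rule | any one of four | any one of four boxes (non-serious) |
| Size | 10 cm or more | same |
| Daily activities | "Impacting daily activities" | "Prevents daily activities" |
| Skin damage | ulceration or necrosis | same |
| Surgery | operation required | same |
| Duration | longer than 24 hours | 24 hours or more, or ongoing |
| Serious ISRs | no separate route | separate route |

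The SAP is equal to or slightly broader than the protocol on every row except daily activities.

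**2. Do the two verbs mean the same thing?** The intensity scale in protocol 10.3 (Appendix 3) separates them. Moderate is "An event that causes sufficient discomfort and interferes with normal everyday activities". Severe is "An event that prevents normal everyday activities". An event that interferes with activities without preventing them has an impact on them, so it meets the protocol's ISR criterion but not the SAP's wording.

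**3. A test case.** Take a non-serious reaction 6 cm across, lasting 3 days, with no ulceration, necrosis or operation, that limits daily tasks but does not prevent them.
- Protocol 8.3.1: over 24 hours, one criterion met, so it is an AESI with notification within 24 hours.
- SAP Table 4 as worded: the duration is met, but no box applies, so it is outside the AESI category.

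**4. What the result depends on.** Table 4 counts ticked boxes, and the Complementary Form is not in the documents.
- If the form's box is worded and completed as *impacting*, the derivation picks up the test case. Table 4 then merely mislabels the box.
- If the box is worded or completed as *prevents*, the test case is left out. Rewording Table 4 would not recover it, because that form would not hold the information.

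Either way, one of the texts needs correcting.

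**5. Where the omitted events still appear.** Table 4 has a separate grouping of all injection site reactions, and SAP 2.4.5.1 tabulates all TEAEs by preferred term and by maximal severity and lists every TEAE. These outputs retain the events but do not single out those that met the protocol's AESI definition.

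**The case against.** **The SAP was given this task.** Protocol Table 15 leaves the definitions of AESIs, and the way they are identified, to the SAP. Silence in SAP 1.5 is therefore weaker evidence of an undeclared change than it first seems, and a reader who infers that the SAP broke a rule goes further than the text allows. The delegation does not remove the conflict, however. Section 8.3.1 already defines this event for sites and says: "Adverse events of special interest may be added, modified or removed during a study by protocol amendment".

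**The intensity scale cuts both ways.** The AESI is called a *severe* ISR, and on the general scale severe means that activities are prevented. Table 4 may follow that scale, so some of the tension lies inside the protocol. That is fair, but the note in 8.3.1 gives its own ISR-specific meaning for reporting, and sites work to that note.

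**Table 4 is a search method.** Other rows also differ from site reporting: the ALT thresholds become a standardised MedDRA query, and hypersensitivity is a query followed by blinded medical review. One-to-one agreement with site reports is not promised. The ISR row is different in kind, though: it reproduces the protocol's criteria item by item and departs in one.

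**Stronger readings that the documents do not support.**
- *Only ISRs that prevent activities count.* No: this is one of four alternative boxes, and serious ISRs qualify separately.
- *The events disappear from the report.* No, as step 5 of the working shows. The secondary safety endpoints, TEAEs and SAEs, are unchanged.
- *The Kaplan-Meier plots and ADA-by-safety summaries will be understated.* SAP 2.4.5.1 produces plots only for categories with at least 5 events in a treatment group, and SAP 2.4.7.2 says only that the ADA-safety association may be explored. Neither output is certain to exist for this category.
- *The duration rule is also wrong.* It is slightly broader than the protocol's, so aligning it could only narrow capture.

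**Conclusion.** The inconsistency is real. As worded, SAP Table 4 leaves out of the AESI category those non-serious ISRs lasting over 24 hours whose sole qualifying feature is an impact on daily activities short of preventing them. Sites must report these same events as AESIs. Whether any are lost in practice depends on how the Complementary Form's box is worded and completed, which the documents do not show.

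The size cannot be given. The documents contain no ISR rates, and the number affected could be zero. The effect is confined to one AESI category in a descriptive safety analysis. No efficacy result or TEAE or SAE endpoint is touched. The point is a modest one, worth settling because the correction is cheap and because the AESI line would otherwise describe a different event from the one the protocol defines. Nothing here says which threshold is clinically right.

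**What to change.** Before database lock, reconcile protocol 8.3.1, SAP Table 4 and the Injection Site Reaction Complementary Form, so that the AESI category captures the event sites are told to report.

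- Check the form first. If its box already records impact on daily activities, correct the label in Table 4.
- If the form records only prevention, also count in the category every ISR that the investigator reported as an AESI. Protocol 8.3.1 has these reported through eCRF screens, so no new data collection should be needed.
- Keep the SAP's duration rule of 24 hours or more, or ongoing.
- If the narrower event is intended, make that change by the route 8.3.1 itself sets out and declare it in the SAP.

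The cost is one wording change and, at most, one extra derivation condition. The downside is that the reported AESI incidence may rise.
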